4.2.11 CCI

4.2.11.1 Definition

The CCI is an CCI measurement used to assess CCI or for older individuals who are CCI .

The total scale is scored from CCI

The scale has CCI , and each is assigned a score of CCI . In this study, the CCI scale will be completed by the CCI at the time of study entry (date of signature of consent) or those who, in the opinion of the Investigator, are CCI .

A copy of the CCI questionnaire is provided in CSP Appendix J 1. The CCI questionnaire will be completed daily in the evening for 7 days after the visits specified in the CSP.

4.2.11.2 Derivations

For each scheduled visit, the weekly average scores will be derived for each item and total score. At each scheduled visit, the CCI questionnaire needs to be completed at least 4

times over 7 days for all **CCI**; otherwise, the weekly average score will not be computed.

The change from baseline values for the weekly average total scale and item scores will be classified according to following categories:

- Worsened **CCI** points compared to baseline
- Worsened **CCI** points compared to baseline
- Worsened **CCI** point compared to baseline
- Stable **CCI**
- Improved **CCI** point compared to baseline
- Improved **CCI** points compared to baseline
- Improved **CCI** points compared to baseline

For the individual items, the categories Worsened **CCI** points and Improved **CCI** points are not applicable.

The post-baseline changes in the total score will be classified as improvement/no change/deterioration compared to baseline scores at each scheduled visit using the CMT reported in the literature (**CCI**) as follows:

- Improvement: absolute change from baseline **CCI** points
- Deterioration: absolute change from baseline **CCI** points
- No change: absolute change from baseline **CCI** points

CCI

CCI will be based on two related components: **CCI**.

Two definitions for the **CCI** will be considered.

The primary definition will include only participants with a **CCI** weekly average score **CCI** points at baseline and will be defined as a decrease of **CCI** points in score without an increase in **CCI** (eg, increase of at least 1 category in the **CCI** category [moving from a score of 0 to a score of 1], see below for definition).

A secondary definition of **CCI** will be considered to also include the asymptomatic participants as follows:

- For participants with **CCI** [redacted] weekly average score **cci** [redacted] points at baseline, **CCI** [redacted] will be defined as a decrease of **cci** [redacted] points in score without an increase in the **CCI** [redacted] score; OR
- For participants with a **CCI** [redacted] weekly average score **cci** [redacted] points AND an **CCI** [redacted] score **cci** [redacted] points at baseline, **CCI** [redacted] will be defined as stable (or reduced) **CCI** [redacted] score compared to baseline AND a decrease of at least 1 level in the **CCI** [redacted] category.

CCI

Information on all CCI [REDACTED] by participants in CCI [REDACTED] will be collected on the CCI [REDACTED] as well as on the CCI [REDACTED]. A modified CCI [REDACTED] CCI [REDACTED] will be used to quantify and score CCI [REDACTED] in the study by the AZ clinical team. The additional class of 2 is added to include typical CCI [REDACTED] used by NF1-PN participants.

For this study, the following categories in Table 12 will be used in the analysis:

An increase of 1 point or more compared to baseline (represents an increase to a CCI CCI CCI score.) is defined as an increase in the CCI score.

CCI [REDACTED] within 7 days from the first questionnaire CCI [REDACTED] completion date will be considered to assess CCI [REDACTED]. If a participant CCI [REDACTED] of a different score within the same period the higher score precedes, for example, if a participant CCI [REDACTED] of score 1 and one of score 3, score 3 will be considered for the relevant period.

4.2.11.3 Analysis of CCI

Summaries for cumulative participant disposition and compliance over time (defined in Section 3.3.9 and 3.3.10, respectively) by each scheduled visit will be reported. Summary statistics will be presented by cohort and total.

A summary table with descriptive statistics for the absolute values and change from baseline in the weekly average total score will be presented for each scheduled visit.

Counts and percentages for each change from baseline category for the weekly average total score at each scheduled visit will be provided.

Counts and percentages for category improvement/no change/deterioration for the weekly average total score at each scheduled visit will be provided.

Change from baseline in the weekly average total scores will be analysed using a REML-based MMRM (as described in Section 4.2.10.4). usingWithin each cohort, the corresponding baseline value rather than baseline CCI score will be used.

Counts and percentages for CCI at each scheduled visit will be provided.

All CCI data will be fully listed, including individual items, total scores, and weekly averages.

Data will be summarised and analysed using the safety analysis set.

4.2.12 CCI

4.2.12.1 Definition

The CCI is a CCI measure of CCI. In this study, the CCI will be used to assess CCI in children aged CCI years at the time of study entry (date of signature of consent) CCI daily in the evening according to the schedule specified in the CSP. CCI are presented to the child, who will then CCI and give a score.

A copy of the CCI questionnaire is provided in CSP Appendix J 2. The CCI questionnaire will be completed daily in the evening for 7 days prior to each visit specified in the CSP.

4.2.12.2 Derivation

For each scheduled visit, the weekly average score will be derived. At each scheduled visit, the CCI questionnaire needs to be completed at least 4 times over 7 days; otherwise, the weekly average score will not be computed.

The change from baseline values will be classified according to following categories:

- Worsened CCI points compared to baseline
- Worsened CCI points compared to baseline
- Worsened CCI points compared to baseline
- Stable
- Improved CCI points compared to baseline
- Improved CCI points compared to baseline
- Improved CCI points compared to baseline

The post-baseline changes in the weekly average total scores will be classified as improvement/no change/deterioration compared to baseline scores at each scheduled visit using the CMT reported in the literature (CCI) as follows:

- Improvement: absolute change from baseline CCI points
- Deterioration: absolute change from baseline CCI points
- No change: absolute change from baseline CCI points

CCI

The derivation of the CCI is the same as described in Section 4.2.11.2 with the use of the CCI score instead of the CCI score.

4.2.12.3 Analysis of CCI

Summaries for cumulative participant disposition and compliance over time (defined in Section 3.3.9 and 3.3.10, respectively) by each scheduled visit will be reported. Summary statistics will be presented by cohort and total.

A summary table with descriptive statistics for the absolute values and change from baseline in the weekly average total score will be presented for each scheduled visit.

Counts and percentages for each change from baseline category for the weekly average total score at each scheduled visit will be provided.

Counts and percentages for category improvement/no change/deterioration for the weekly average total score at each scheduled visit will be provided.

Change from baseline in the weekly averages will be analysed using a REML-based MMRM (as described in Section 4.2.10.4), and considering CCI score at baseline rather than baseline CCI score.

Counts and percentages for CCI [REDACTED] at each scheduled visit will be provided.

All CCI [REDACTED] data will be fully listed, including individual scores and change from baseline.

Data will be summarised and analysed using the safety analysis set.

4.2.13 CCI

4.2.13.1 Definition

The CCI [REDACTED] instrument is a CCI [REDACTED] measure used to assess CCI [REDACTED]

A copy of the CCI [REDACTED] questionnaire is provided in CSP Appendix J 3. The CCI [REDACTED] questionnaire will be performed at visits specified in the CSP.

4.2.13.2 Analysis of CCI

Summaries for cumulative participant disposition and compliance over time (defined in Section 3.3.9 and 3.3.10, respectively) by each scheduled visit will be reported. Summary statistics will be presented by cohort and total.

Counts and percentages for each response option at each scheduled visit will be provided along with the corresponding bar chart.

All CCI [REDACTED] data will be listed.

Data will be summarised and analysed using the safety analysis set.

4.2.14 CCI

4.2.14.1 Definition

The CCI [REDACTED] is a CCI [REDACTED] measure used to CCI [REDACTED]

CCI [REDACTED]

A copy of the CCI [REDACTED] questionnaire is provided in CSP Appendix J4. The CCI [REDACTED] questionnaire will be performed at visits specified in the CSP.

4.2.14.2 Derivation

The change from baseline values will be classified according to the following categories:

- Worsened CCI compared to baseline
- Worsened CCI compared to baseline
- Worsened CCI compared to baseline
- No change
- Improved CCI compared to baseline
- Improved CCI compared to baseline
- Improved CCI compared to baseline

4.2.14.3 Analysis of CCI

Summaries for cumulative participant disposition and compliance over time (defined in Section 3.3.9 and 3.3.10, respectively) by each scheduled visit will be reported. Summary statistics will be presented by cohort and total.

A summary table with descriptive statistics for the absolute values and change from baseline will be presented for each scheduled visit.

Counts and percentages for each response option at each scheduled visit will be provided along with a corresponding bar chart.

Counts and percentages for each change from baseline category at each scheduled visit will be provided.

All CCI data will be listed.

Data will be summarised and analysed using the safety analysis set.

4.2.15 CCI

4.2.15.1 Definition

A CCI will be used to ensure that CCI information on CCI will be collected, including CCI. The survey will be completed by CCI daily on paper in the evening for 7 days prior to the visits specified in the CSP and verified by the Investigator or delegate.

4.2.15.2 Analysis of the CCI

Descriptive statistics for the CCI at each scheduled visit will be provided, CCI. Summary statistics will be presented by cohort and total.

All **CCI** data will be listed.

Data will be summarised and analysed using the safety analysis set.

4.3 Pharmacodynamic Endpoint(s)

This section covers details related to pharmacodynamic endpoints and analyses.

4.3.1 Analysis

Where possible, optional blood samples for exploratory analysis of pharmacodynamic biomarkers in PBMCs can be taken during Cycle 1 Day 1. This analysis includes, but may not be limited to, pERK inhibition. This would require additional blood volume on a PK profile day in addition to the volume required for PK samples and safety samples.

In line with the European Condition requirement that blood volume should not exceed 1% of the total blood volume at any single time, the samples for pERK can only be collected in participants ≥ 27 kg. For a participant who is 6 years old, this would mean that they would have to be approaching the 98th percentile on the UK-WHO growth chart ([UK WHO Growth Chart](#)). It is therefore considered these samples would be collected only in the oldest and largest of children.

4.3.2 Sampling schedule

Samples will be taken pre-dose within 10 minutes prior to dosing, at 1 and 3 hours post-dose (± 15 minutes), and at 18 to 24 hours post-dose as described in the CSP Table 16.

4.3.3 Presentation

Not applicable, at the moment to write the current SAP version, with all subjects included. Cycle 1 Week 1 PD data have not been collected and no analysis will be reported.

4.4 Pharmacokinetics

4.4.1 Calculation or Derivation of Pharmacokinetic Parameters

The plasma PK parameters for selumetinib and N-desmethyl selumetinib will be derived using non compartmental methods **CCI**

CCI

The PK parameters will be derived **CCI**

PK analysis will be carried out, where data allow, using actual elapsed times determined from the PK sampling and dosing times recorded in the database. If actual elapsed times are missing, nominal times may be used. Nominal sampling times may be used for any agreed interim PK parameter calculations.

Where data allow, the following single-dose PK parameters (Table 13) for selumetinib and N-desmethyl selumetinib will be derived from Cycle 1 Day 1 plasma concentrations.

Table 13 Single-Dose Pharmacokinetic Parameters

PK parameter	Description
Cmax	Maximum observed concentration
tmax	Time to reach the maximum observed concentration
AUC0-6	Partial area under the concentration-time curve from time 0 to 6 hours
AUC0-12	Partial area under the concentration-time curve from time 0 to 12 hours
AUC0-24	Partial area under the concentration-time curve from time 0 to 24 hours
AUClast	Area under the concentration-time curve from 0 to the last quantifiable concentration
CL/F	Apparent total body clearance of drug from plasma after extravascular administration (selumetinib only)
Vz/F	Volume of distribution (apparent) based on the terminal phase following extravascular administration (selumetinib only)
t½λz	Half-life associated with the terminal slope of the concentration-time curve
MPAUC0-6	Metabolite:parent ratio based on AUC0-6
MPAUC0-12	Metabolite:parent ratio based on AUC0-12
MPAUC0-24	Metabolite:parent ratio based on AUC0-24
MPCmax	Metabolite:parent ratio based on Cmax

In addition, where data allow, the following multiple-dose PK parameters (Table 14) for selumetinib and N-desmethyl selumetinib will be derived from CCI

CCI

Table 14 Multiple-Dose Pharmacokinetic Parameters

PK parameter	Description
Cmax	Maximum observed concentration
tmax	Time to reach the maximum observed concentration
AUC0-6	Partial area under the concentration-time curve from time 0 to 6 hours
AUC0-12	Partial area under the concentration-time curve from time 0 to 12 hours

AUClast	Area under the concentration-time curve from 0 to the last quantifiable concentration
CL/F	Apparent total body clearance of drug from plasma after extravascular administration (selumetinib only)
Vss/F	Volume of distribution (apparent) at steady state following extravascular administration (selumetinib only)
MPAUC0-6	Metabolite:parent ratio based on AUC0-6
MPAUC0-12	Metabolite:parent ratio based on AUC0-12
MPCmax	Metabolite:parent ratio based on Cmax
RacAUC0-12	Accumulation ratio for AUC0-12
RacCmax	Accumulation ratio for Cmax

The diagnostic PK parameters in [Table 15](#) will be provided, where appropriate.

Table 15 Diagnostic PK parameters

PK parameter	Description
λ_z	Terminal elimination rate constant
λ_z upper	Lower (earlier) time used for λ_z determination
λ_z lower	Upper (later) time used for λ_z determination
λ_zN	Number of data points used for λ_z determination
Rsq adj	Statistical measure of fit for the regression used for λ_z determination, adjusted for the number of used data points
λ_z span ratio	Time period over which λ_z was determined as a ratio of $t_{1/2}/\lambda_z$
tlast	Time of last observed (quantifiable) concentration.
AUCextr (%)	Extrapolated area under the curve from tlast to infinity
$t_{1/2}/\lambda_z$	Half-life associated with the terminal slope of the concentration-time curve

PK, pharmacokinetic.

In addition, for the PK profiles collected on [CCI](#)

2 [CCI](#)

BSA normalised (BN) PK parameters and dose normalised (DN) PK parameters for AUC0-6, AUC0-12, AUClast, and Cmax will be derived by programming in SAS for all analytes by dividing the relevant parameters by the

participant's BSA value or the actual administered dose in milligrams (mg), respectively, on the corresponding PK visit.

In addition, dose by BSA normalised (DBN) AUC0-6, AUC0-12, AUClast, and Cmax will be derived by programming in SAS for all analytes by dividing the relevant parameters by the participant's actual administered dose in mg/m² on the corresponding PK visit. For the participants who transition to capsule formulation, the ratio of granule:capsule formulation will be determined by programming in SAS for each of these BN and DN parameters.

Additional PK parameters may be determined, where appropriate.

If an entire concentration-time profile is not quantifiable, the profile will be excluded from the PK analysis.

The minimum requirement for the calculation of AUC values will be the inclusion of at least

3 consecutive quantifiable concentrations. Where there are only 3 quantifiable concentrations, at least one of these should follow the peak concentration.

The same analysis as described in Section 4.2.1.1 and Section 4.2.1.2 for the primary endpoint will be performed for N-desmethyl selumetinib.

Details of CCI [REDACTED] and CCI [REDACTED] analyses will be described in a separate PK modelling analysis plan, which will be finalized before the database lock and is not in scope of this SAP.

4.4.2 Presentation of Pharmacokinetic Data

The plasma selumetinib and N-desmethyl selumetinib concentrations and the PK parameters will be listed and presented in tabular and graphical form, as appropriate, according to the CCI [REDACTED]

[REDACTED], which include applicable descriptive statistics, defined handling of individual concentrations below the LLOQ, and precision/rounding rules for concentrations and PK parameter data.

Exclusion of concentration and/or parameter data from PK summaries may apply; this will be flagged in the listings with the reason(s) for exclusion.

4.4.2.1 Plasma Concentrations

Selumetinib and N-desmethyl selumetinib plasma concentrations for each scheduled time point will be summarised using appropriate descriptive statistics based on the PK Analysis Set. The summary tables will be presented as follows:

CCI [REDACTED] By analyte, BSA group, and PK serial sampling day (CCI [REDACTED])

CCI

CCI By cohort (Cohort 1, Cohort 2, total global and Japan cohort), analyte, and PK serial sampling day CCI

The PK concentrations for the Japan Cohort will be summarised CCI

Three observations > LLOQ are required as a minimum for a plasma concentration to be summarised for each dose. Less than three observations > LLOQ are presented as a minimum and maximum with the other summary statistics as NC.

The on-treatment BSA group will be used to present plasma concentrations by BSA group (ie, the BSA group the participant falls within at the relevant scheduled PK sample timepoint from Cycle 1 through Cycle 25). The on-treatment BSA group categories are the same as those defined for the baseline BSA group (see Section 4.1.5.1).

A listing of concentration versus scheduled time data will be presented by cohort, analyte, BSA group, and PK serial sampling day for the PK Analysis Set. A listing of all concentration-time data (ie, PK scheduled times, actual sample collection times, sample actual relative times, as well as derived sampling time deviations) will be presented for the safety analysis set.

Trough concentrations collected at pre-dose on Day 1 of Cycle 5, 13, and 25 will be listed only.

4.4.2.2 Pharmacokinetic Parameters

Individual PK parameters for selumetinib and N-desmethyl selumetinib will be listed and summarised based on the PK Analysis Set. The summary tables will be presented as follows:

- By analyte, BSA group, and PK Day for the total global cohort
- By cohort (Cohort 1, Cohort 2, total global and Japan cohort), analyte and PK Day

The PK parameters for the Japan Cohort will be summarised CCI

CCI

The ratio granule: capsule formulation for dose normalised parameters will be listed and summarised separately, based on the PK Analysis Set. The summary tables will be presented:

- By analyte, BSA group, and PK Day for the total global cohort
- By cohort (Cohort 1, Cohort 2, total global and Japan cohort), analyte and PK Day

Three observations (> LLOQ if Cmax) are required as a minimum for a PK parameter to be summarised for each dose. Less than three observations (> LLOQ if Cmax) will be presented as a minimum and maximum with the other summary statistics as NC.

The on-treatment BSA group will be used to present plasma concentrations by BSA group (ie the BSA group the participant falls within at the relevant scheduled PK sample timepoint from Cycle 1 through to Cycle 25). The on-treatment BSA group categories are the same as those defined for the baseline BSA group (see Section 4.1.5.1).

4.4.2.3 Graphical Presentation

Individual concentration-time data will be graphically presented on linear and semilogarithmic scales for the PK Analysis Set. Each individual's plot will include the concentration versus actual time profiles from CCI [REDACTED].

Combined individual concentration versus actual time profiles will be plotted on both the linear and semi-logarithmic scale with all participants overlaid, based on the PK Analysis Set. The combined individual concentrations plots will be separated as follows:

- By analyte, BSA group and PK serial sampling day CCI [REDACTED] after transitioning to capsule dosing) for the total global cohort
- By analyte, cohort (Cohort 1, Cohort 2, total global and Japan cohort), and PK serial sampling day (CCI [REDACTED] after transitioning to capsule dosing)

CCI [REDACTED]

Figures for the geometric mean concentration-time data will be presented on both a linear with (*/gSD) error bars and a semi-logarithmic scale (no error bars), separately for CCI [REDACTED] after transitioning to capsule dosing, based on the PK Analysis Set. Two group of figures will be presented, with the following variables overlaid on the same plot:

- Analyte, BSA group for the total global cohort
- Analyte and cohort (Cohort 1, Cohort 2, total global and Japan cohort)

CCI [REDACTED]

In addition, geometric mean concentration-time data will be presented on both a linear with (*/gSD) error bars and a semi-logarithmic scale (no error bars) for the Japan Cohort with the Global Cohorts overlaid on the same plot with different symbols for each cohort, based on the PK Analysis Set, if data permits. The figures will be separated as follows:

- By analyte and PK serial sampling day (CC1 after transitioning to capsule dosing)

The on-treatment BSA group will be used to present plasma concentrations by BSA group (ie, the BSA group the participant falls within at the relevant scheduled PK sample timepoint from Cycle 1 through Cycle 25). The on-treatment BSA group categories are the same as those defined for the baseline BSA group (see Section 4.1.5.1).

For box and whisker plots of the PK parameters selumetinib and N-desmethyl selumetinib Cmax and AUC0-12 versus cohort (Global and Japan), the BSA group will be plotted separately by parameter and by CC1 after transitioning to capsule dosing for the total global cohort.

Scatter figures with age (years) on the x-axis and PK parameter on the y-axis will be presented to evaluate the effect of age on PK, based on the PK Analysis Set. These scatter figures will be shown for the following:

- Selumetinib single-dose Cmax, AUC0-6, AUC0-12, AUC0-24, AUClast, and tmax
- N-desmethyl selumetinib single-dose Cmax, AUC0-6, AUC0-12, AUClast, AUC024, and tmax
- Selumetinib multiple-dose Cmax, tmax, AUC0-6, AUC0-12, and AUClast
- N-desmethyl selumetinib multiple-dose Cmax, tmax, AUC0-6, AUC0-12, and AUClast

The scatter figures will only be presented for the Global Cohort and will include the geometric mean for Cohort 1, Cohort 2, and Total in Global.

All individual and summary PK figures will be presented separately by analyte.

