## 2.3.2 Benefit Assessment

Selumetinib capsules have been shown to be effective in the treatment of paediatric patients with NF1 who have symptomatic, inoperable PN and are approved in the US for the treatment of paediatric patients aged  $\geq 2$  years of age. In the pivotal SPRINT study, selumetinib showed a durable and sustained tumour shrinkage, with an overall response rate of 66%, alongside improvement in clinical outcomes (Gross et al 2020). There are no other approved treatments for NF1-PN. It has been demonstrated previously that younger NF1-PN patients have faster growing PNs (Akshintala et al 2020, Nguyen et al 2012, Tucker et al 2009). An analysis of patient response to selumetinib treatment in the SPRINT study by age group shows that there is a numerically higher ORR in the youngest age group ( $\geq 3$  to 7 years), although benefit was observed in all ages. Therefore, it is likely that the participants in this study might derive clinical benefit from treatment with the granule formulation of selumetinib.

As shown from the relative bioavailability study (D1532C00089; Study 89), food is not expected to affect the primary PK analysis variable AUC. Without the fasting restrictions, it is intended that the granule formulation dosing posology will be more convenient and pragmatic for this younger patient group.

Participants in the study may therefore benefit from treatment. Following the end of the study, a mechanism will be in place to ensure that participants will be able to continue taking selumetinib as long as they derive clinical benefit, as judged by the investigator.

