# 4.2 Scientific Rationale for Study Design

The efficacy of selumetinib capsule in the treatment of NF1-related symptomatic, inoperable PN in paediatric participants was demonstrated in the SPRINT study in which selumetinib was taken bid under fasted conditions (fast for 2 hours before each dose and one hour after each dose). Safety data from this study showed that selumetinib has a generally predictable and manageable safety profile in this population. Study D1346C00013 (NCT04495127) demonstrated selumetinib capsule monotherapy is well tolerated and has a manageable safety profile in all paediatric Japanese patients with NF1-related PN, and that the PK profile appeared to be similar to that observed in the pivotal SPRINT study. Following a single mg/m^2, selumetinib geometric mean ratio (90% CI) for Cmax and AUC0-12 were **CC** and **CC** respectively, for Study 13 compared to SPRINT Phase II Stratum 1. Given the considerable overlap of these exposures and that there was no clear relationship observed for exposure and safety or efficacy, these differences are not considered clinically relevant. There is no dose adjustment required for Japanese patients; the recommended dose is **C** mg/m^2.

Selumetinib is currently available in a capsule formulation which precludes administration to children with a BSA of  $< 0.55 \text{ m}^2$  or very young children who may have difficulty swallowing capsules. Therefore, AstraZeneca has developed an alternative age appropriate granule formulation of selumetinib for infants and young children aged  $\ge 1$  to < 7 years which is contained within a sprinkle capsule.

A relative bioavailability study (D1532C00089; Study 89) has been conducted in healthy adult volunteers with both selumetinib commercial capsule formulation and the granule formulation; both formulations were considered to have a similar extent of exposure (AUC) with a geometric mean ratio (90% CI) of 0.86 (0.81, 0.92). (AstraZeneca notes the selumetinib content for the granule formulation batch used in Study 89 was % and would contribute to the lower exposure determined for the granule, whereas the selumetinib content in the current study is expected to be close to %.) In addition, the effect of a low-fat meal on the granule formulation was investigated; no food effect was observed on the overall extent of exposure (AUC) with a geometric mean ratio (90% CI) of 0.97 (0.91, 1.02).

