# Capsule Dose Schema for Selumetinib 25 mg/m^2 bid

bid, twice daily; BSA, body surface area.

Granules from the sprinkle capsule should be mixed with a dosing vehicle prior to administration. Detailed instructions will be provided in the IMP handling instruction document or an equivalent document.

The time and content of meals on intensive PK sampling days (Cycle 1 Day 1, Cycle 2 Day 1 and, should the participant transition to capsule formulation, capsule dosing Day 7) should be recorded in source data.

Selumetinib granules are administered twice a day, approximately 12 hours apart. For participants aged  $\geq 1$  to < 4 years selumetinib granules can be taken without regard to food.

For participants aged  $\geq$  4 to < 7 years, on intensive PK sampling days (Cycle 1, Day 1 and Cycle 2, Day 1), selumetinib granules must be taken on an empty stomach (no food or drink other than water for 2 hours before and one hour after dosing, with the exception of vehicle and water to cleanse the palate). On other study treatment days selumetinib may be taken without regard to food.

Where capsules are taken, selumetinib capsules should be swallowed whole with a glassful of water twice a day, approximately 12 hours apart, on an empty stomach (no food or drink other than water for 2 hours prior to dosing and one hour after dosing).

If a dose of selumetinib is missed, it should only be taken if it is more than 6 hours until the next scheduled dose. Do not take an additional dose if vomiting occurs after selumetinib administration but continue with the next scheduled dose.

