	 Safety samples are perfo depending on the Institut blood required.	formed by local lab, the tion. Each site is advis	refore actual ve ed to minimise	olumes will vary the amount of				
	 Optional pharmacodynamic samples which are collected only in patients $\geq 27$ Kg.							
	Investigators participating in the SPRINKLE study will use their discretion in the method of collecting biological samples to ensure that it is the least invasive manner for their patient. To minimise the number of punctures, the schedule of assessments is designed so that safety and PK samples can be taken at the same timepoint. PK samples can be taken using venous catheter to minimise the number of punctures, and AstraZeneca recommends that this is the approach Investigators use in order to minimise burden on the patient. Additionally sites are advised to use local measures such as local anaesthesia to reduce the discomfort of the blood sampling.							
	The intensive PK days of Cycle 1 Day 1, and Cycle 2 Day 1 require 9, and 8 samples respectively to be taken within a 24 hour period. This number of samples is required so that we can estimate the pharmacokinetic profile and obtain the AUC values which is a primary objective of the study. On intensive PK sampling days, participants aged $\geq 1$ to < 4 years can take selumetinib granules with or without food, but participants aged $\geq 4$ to < 7 years are required to take selumetinib granules on an empty stomach. The flexibility for the younger children may lead to variability in the Cmax and tmax as food intake is known to reduce the rate of absorption of selumetinib. Adequate numbers of samples are therefore required to capture the tmax of the plasma concentrations under these differing conditions. The final statistical analysis will compare the SPRINKLE study AUC0-12 (patients aged proved dose of 25 mg/m  , and reducing the number of samples further could potentially lead to an underestimation of exposure which could compromise the study endpoint.							

Section # and Name	Description of Change with Reason

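### The food rule on granule PK days changes at age 4, so the planned age figures cannot separate age from food for Cmax and tmax unless food state is shown

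*SAP*

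**What the plan says.** Protocol Section 6.1.1 sets two food rules for Cycle 1 Day 1 and Cycle 2 Day 1. For ages 4 to under 7, "selumetinib granules must be taken on an empty stomach", defined as nothing but water for 2 hours before and 1 hour after the dose, apart from the dosing vehicle. For ages 1 to under 4, "selumetinib granules can be taken without regard to food". Age 4 is also the line between Cohort 1 and Cohort 2. The same section asks sites to record in source data "The time and content of meals on intensive PK sampling days".

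The German addendum in Appendix G states that food slows selumetinib absorption. It adds: "The flexibility for the younger children may lead to variability in the Cmax and tmax". On extent of exposure, Protocol Section 2.3.2 says that "food is not expected to affect the primary PK analysis variable AUC". Section 4.2 gives the supporting granule result from Study 89 in healthy adults, a fed/fasted geometric mean ratio of 0.97 (90% CI 0.91 to 1.02).

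SAP Section 4.4.2.3 plans scatter figures with age on the x-axis, which "will be presented to evaluate the effect of age on PK, based on the PK Analysis Set". They cover Cmax, tmax, AUC0-6, AUC0-12 and AUClast, plus AUC0-24 after the single dose, and carry the geometric means of Cohort 1, Cohort 2 and the global total. SAP Section 4.4.2.2 tabulates PK parameters by cohort. The readable SAP text names no fed/fasted variable, marker, stratum or listing, and Protocol Section 9 specifies none.

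**The concern.** The figures are meant to show what age does to PK, but the conditions of measurement also change at age 4. Every child above that age should be fasted, and any child below it may have eaten. A lower Cmax or later tmax in Cohort 2 is the pattern that slower absorption after food would give. Read from these plots, it could be taken for an effect of age on absorption, or food could hide a real one. The question matters because Protocol Section 4.3 builds the low-BSA doses on a model that allows for age-related changes in absorption and metabolism under 3 years. The sponsor anticipated food-related variation in Cmax and tmax and answered it through sampling density, but did not carry it into the specified analysis.

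**Working it through.** **Inputs from the documents**
- Food rule on granule PK days: fasted at ages 4 to under 7, unrestricted at ages 1 to under 4 (Protocol 6.1.1).
- Granule fed/fasted ratio for AUC: 0.97, 90% CI 0.91 to 1.02 (Protocol 4.2).
- Granule fed/fasted ratio for Cmax: not given.

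**Assumptions**
- Fraction f of Cohort 2 that is fed at the PK dose: 0.5 as the working case, with 0.25 and 1 as the range.
- Fed/fasted ratio r for Cmax: 0.5 to 0.8.
- All of Cohort 1 is fasted, and there is no true age effect.

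**The protocol's figure.** The AUC ratio cannot be re-derived without the Study 89 data. Its consistency can be checked: the geometric midpoint of the interval is √(0.91 × 1.02) = 0.963. Allowing for rounding of the limits, it lies between √(0.905 × 1.015) = 0.958 and √(0.915 × 1.025) = 0.968. A stated 0.97, which covers 0.965 to 0.975, is compatible with that.

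**Formula.** With no age effect, the Cohort 2 to Cohort 1 ratio of geometric means produced by food alone is r^f.

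**AUC0-12** (applying the adult AUC ratio)

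| f | r = 0.91 | r = 0.97 | r = 1.02 |
|---|---|---|---|
| 0.25 | 0.977 | 0.992 | 1.005 |
| 0.5 | 0.954 | 0.985 | 1.010 |
| 1 | 0.910 | 0.970 | 1.020 |

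At f = 0.5 the shift is -1.5%, with a range from -4.6% to +1.0%. If every younger child ate, it would be -3%, with a range from -9% to +2%.

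**Cmax** (assumed r)

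| f | r = 0.5 | r = 0.65 | r = 0.8 |
|---|---|---|---|
| 0.25 | 0.841 | 0.898 | 0.946 |
| 0.5 | 0.707 | 0.806 | 0.894 |
| 1 | 0.500 | 0.650 | 0.800 |

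At f = 0.5, Cohort 2 would sit 11% (r = 0.8), 19% (r = 0.65) or 29% (r = 0.5) below Cohort 1 with no effect of age. With a quarter fed, the span is 5% to 16%.

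**tmax and AUC0-6.** The documents give no size for either. Slower absorption would move tmax later. It would probably also lower AUC0-6 by shifting exposure out of the first six hours, but that last step is inference and is not stated in the documents.

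**What the design still identifies.** Because all of Cohort 1 is fasted, an age trend within Cohort 1 is free of the food rule. Fed and fasted children can coexist within Cohort 2, so the two states can be compared there if they are recorded.

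**The case against.** The best defence is that the primary endpoint is single-dose AUC0-12, estimated by age group and set against SPRINT (Protocol 9.1), and that the protocol has already dealt with food for AUC. The granules are also meant to be given without fasting restrictions (Protocol 2.3.2), so Cohort 2 is measured as the product would be used. On that view feeding belongs to the exposure of interest and is not merely a nuisance. Both points stand for the primary comparison. They do not rescue the age figures, where one cohort is fasted by rule and the other is not, and where Cmax and tmax are plotted alongside AUC.

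Four stronger readings are tempting but lack support.
- A reader might infer that the meal records are never used, or cannot be. The documents do not show this. Separate modelling will examine the effect of a redacted factor on granule and capsule PK under a plan that is not supplied. The CRF is not supplied either. Protocol Section 9.4.1 also says in general terms that study data will be listed and summarised as appropriate. That statement commits to no food analysis, but it rules none out.
- A reader might infer that an AUC0-12 difference from SPRINT, whose patients were fasted, could not be interpreted. The protocol's own ratio limits the food contribution to a few per cent. The caveat is its source, healthy adults and, in the protocol's words, "In addition, the effect of a low-fat meal on the granule formulation was investigated". Carrying it over to unrestricted meals in toddlers is an assumption, but not evidence of a larger bias.
- A reader might want a false-positive rate for an age slope. The SAP plans scatter figures with geometric means, with no regression or test, so such a rate would describe no planned output.
- A reader might conclude that age statements should rest on fasted children only. Fasted children in Cohort 2 would be self-selected, and willingness to fast may itself vary with age.

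**Conclusion.** The concern holds for the rate-related parameters. Food rule and age group are aligned by design, and no use of food state is specified in the SAP or Protocol Section 9. Cross-cohort differences in Cmax and tmax, and probably AUC0-6, therefore cannot be attributed to age from the planned outputs. The confounding is partial, because younger children may eat but need not.

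For Cmax, the false Cohort 2 deficit would be about 11% to 29%, resting on an assumed fed/fasted ratio of 0.5 to 0.8 and an assumed half of Cohort 2 fed. For AUC0-12 the shift is about -1.5%, within about -5% to +1%, on the same fed share and the adult low-fat-meal ratio. The primary PK conclusion is thus little affected. This is a worthwhile and inexpensive improvement to descriptive outputs on secondary parameters. The contrast concerns granule PK days only, since capsules are taken fasted.

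**What to change.** 1. Confirm whether the meal times recorded on PK days reach the study database. If they do not, transcribe them from source for the Cycle 1 Day 1 and Cycle 2 Day 1 doses.
2. Derive fed or fasted at each granule PK dose from the protocol's own definition (2 hours before, 1 hour after), and list it.
3. In SAP Section 4.4.2.3, give fed and fasted children distinct symbols in the age scatter figures.
4. In SAP Section 4.4.2.2, summarise Cohort 2 Cmax, tmax, AUC0-6 and AUC0-12 by food state, descriptively.
5. Make any statement about age and Cmax or tmax with food state shown beside it.

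The cost is minor data entry, a few extra table rows and a plotting symbol. The fed and fasted cells in Cohort 2 will be small, so the summaries can only describe. Dosing instructions, endpoints and sample size stay as they are.
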